Baseline Period: During a 4-week baseline period, the participants will continue their usual activity but will wear the Garmin and ActivPAL 4 and keep a study diary. We will use this to assess their baseline PA profiles and seizure frequency and to screen for adherence with device and diary use, as participants who have <75% complete days of seizure recording or step data via the Garmin will not be randomized. A 4-week baseline period and self-report of seizures are both standard protocol in epilepsy clinical trials.[45]

Batched enrollment will be utilized to ensure large enough groups for the group coaching exercise intervention. Due to this, the time between visits may vary.

Arm 1 Exercise Intervention:

Participants in this arm will undergo a 12-week physical activity program aimed to achieve the equivalent of 8,000 steps per day (56,000 weekly steps). To ensure uptake, our intervention is rooted in social cognitive theory and led by a trained health coach, trained within the Wake Forest Behavioral Medicine Lab's Behavioral Coaching program, which follows principles of group dynamics, social cognitive theory, and self-determination theory to develop self-efficacy for behavior change, which is instrumental to building lasting behavior.

Participants will meet in small groups of 2-8 participants facilitated by a behavioral coach and, when available, a patient-stakeholder. Following randomization, the behavioral coach will contact the participants in this arm, to set up a time for each weekly video meeting. Each weekly meeting will occur within the coach's locked Webex room using a single link that will be provided to participants digitally via email. In the event of any unforeseen technical difficulties, participants can call into the Webex meeting, but this is not preferred. These sessions are developed using group dynamics principles and founded in social cognitive theory, utilizing the group structure as a tool of behavior change. Participants will act as models to one another, provide an avenue for addressing exercise barriers that arise daily, and foster a sense of accountability toward weekly activity goals.

During each weekly video meeting, the coach and participants will review the timing of the next week's meeting, modifying the timing as needed, and setting reminders if applicable.

Each group session will progress through the following tasks:

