- The study intervention is simple and the weekly step goal is clearly explained to the participant.
- The weekly step goal is individualized, and is created each week during a 1:1 session with the coach while taking into account the participant's individual barriers.
- Participants will be encouraged to seek social support from family and friends and walk with family and friends when able.
- The intervention period is relatively short (only 12 weeks).
- Participants in the control group will be given a personalized physical activity plan if they complete the study
- All participants will be compensated \$50 per visit (4 visits; for total of \$200/participant) to help cover the costs of transportation, parking, and any time away from employment for each research visit.
- Eligibility criteria are designed to exclude participants in poor physical or emotional health for whom adherence may be challenging.
- Study appointment reminders will be given to all participants. Reminders to complete the study diary will be given daily.
- For in-person study visits, the participant will be contacted 1-3 days prior to remind them and confirm the appointment.
- The group coaching format will enhance social support, participant engagement, and add additional resources to help with troubleshooting barriers. When available, a patient-stakeholder will join the coaching session to provide additional social support.

Strategies to support retention:

- Participants in the control group will be given the opportunity to receive a personalized physical activity program if they complete the study.
- Participants will be compensated \$50 per study visit V1-V4
- Study appointment reminders will be given to both groups.

BLINDING

Due to the nature of the intervention, participants will not be blinded as to whether they are in the intervention or control group.

The final analysis of activity data and heart rate variability (HRV) will also be performed by blinded assessors. An unblinded investigator or sub-investigator will gather the data and de-identify the information such that those processing the data will not be privy to which arm is which. The PI will not be blinded in this pilot feasibility study, in order to best track adherence and fidelity and help troubleshoot unexpected barriers.

FOLLOW-UP VISITS

Visit 3, Week 16 End of Intervention:

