At the end of the intervention period, participants will return for post-intervention assessments to include assessments of seizure frequency (Study Diary), seizure severity (Liverpool Seizure Severity Scale), depression(NDDI-E), Review Assurance of the NNDI-E, anxiety (GAD-7), quality of life (QOLIE-31), medication side effects (AEP) cardiorespiratory fitness and mobility (maximum oxygen uptake and 6 minute walk test), sleep (PSQI and from Garmin device) and autonomic tone (heart rate variability).

At the end of the intervention period, participants in arm 1 will be encouraged to continue their current habits. Participants in arm 2 will be offered the opportunity to receive a personalized exercise program. Those in arm 1 will also complete a questionnaire about the acceptability, tolerance and satisfaction with the exercise intervention.

Visit 4, Week 28. Sustainability Follow-up and Study end

This will be a remote visit in order to reduce exposure in the era of COVID-19 as well as improve access for PWE. All outcomes will be re-assessed for sustainability, with the exception of the exercise test, HRV and the 6MWT due to the remote nature of this visit. The risks of excessive in-person visits and transportation issues outweigh the potential benefit of collecting this follow-up data, especially in light of COVID-19. At the end of the visit, all participants will answer an exit questionnaire on their thoughts about the study, what they liked, and what they would change.

All visits will occur either at the Worrel Building or at the Clinical Research Unit (CRU). Due to batched enrollment, time between visits (especially Visits 2 and 3) may vary.

	Visit 0 Telephone Screen	Visit 1 Enrollment Week 0	Visit 2** Randomization Week 4	Intervention Period Week 5-16		Visit 3 End Intervention Week 16	Visit 4 Follow-up Week 28 (remote)
				Exercise	Control		
Review inclusion/exclusion	X	X					
10 meter walk screen		X					
Informed Consent		X					
Vital Signs		X				X	
Collect demographic and baseline medical information		X					

Protocol version:

Template updated 9.24.14

Distribute Study Diary		X					
Distribute Activity Tracker		X					
Collect/Review Study Diary*			X			X	X
Collect/Review data from Garmin			X	X	X	X	X
Review medications and adherence		X	X			X	X
Randomization			X				
Weekly telehealth coaching				X			
Intervention satisfaction questionnaire				X			
Telephone education Q2 weeks					X		
Exercise Test			X			X	

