Questionnaires: PSS, AEP, NDDI-E, Review Assurance of the NNDI-E, GAD-7, QOLIE-31, EXSE, EGS, MOESS, LSSS		X				X	X (with exception of NNDI-E and "Review Assurance of the NNDI-E")
HRV measurement		X	X			X	
6 minute walk test		X				X	
Exit Questions							X

*in addition to review at these visits, the study diary will also be returned daily and reviewed by weekly by a member of the study staff.

**If scheduling is a challenge, V2 can be completed over the telephone with the exercise test being conducted at the first available timepoint and prior to the intervention period

Outcome Measure(s)

1. Primary Objective: Feasibility of the intervention (Adherence and Sustainability)
 - a. Primary Endpoints
 - i. Adherence to the intervention
Adherence will be measured as the number of average daily steps achieved compared to steps assigned during the final 4 weeks of the intervention period
 - ii. Sustainability of the intervention
Sustainability will be measured as the number of average daily steps achieved compared to steps assigned during the final 4 weeks of the maintenance period
2. Secondary Objectives: To evaluate the intensity distribution in the intervention arm
 - a. Secondary Endpoints: time spend in various activity behaviors (measured by the ActivePAL4)
 - i. Time spent sedentary
 - ii. Time spent in light intensity activity
 - iii. Time spent in moderate intensity activity
 - iv. Time spent in vigorous intensity activity
 - v. Acceptability of the Intervention
Participants will answer an exit survey at Visit 4 regarding what they liked about the study and what they did not like, including reasons for missed visits or non-adherence, barriers encountered, and overall satisfaction of various aspects of the study. In addition, arm 1 will answer a questionnaire at the end of the 12 week intervention about the acceptability, tolerance and satisfaction

Protocol version:

Template updated 9.24.14

with the exercise intervention. For the main endpoint, we will use the question “How satisfied were you with the exercise intervention?” with scale of 1=VERY UNSATISFIED, 2=UNSATISFIED, 3=NEUTRAL, 4=SATISFIED, 5=VERY SATISFIED. We will calculate the proportion of subjects who answer 4 or above.

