Efficacy Questionnaire (EXSE)[51], Exercise Goal Setting Questionnaire (EGS)[52], and Multidimensional Expectations for Exercise Scale (MOEES)[53]. These will be given in person at Visits 1 and 3 and remotely via redcap survey at Visit 4.

2.

v. Effects on physical function

1. Autonomic tone: Heart rate variability (HRV)

a. Heart Rate Variability (HRV) measurement: Continuous heart rate will be recorded while the participant is breathing normally in seated position for 10 minutes using Faros 180 heart rate monitor (Bittium Corporation, Oulu, Finland)[54]. Beat to beat intervals (RRI) files will be generated at 1000 Hz via the data acquisition software. The files will be analyzed with Nevrokard HRV software (by Nevrokard Kiauta, d.o.o., Izola, Slovenia). The recordings will be visually inspected to ensure data quality (dropped beats or gross motion artifacts are excluded) and the first 5 minutes of usable tracings will be analyzed. We will obtain measures of HRV in the frequency domain and these measures will be integrated over specified frequency ranges (LF: 0.04-0.15 Hz; HF: 0.15-0.4 Hz). Power of RRI spectra in LF, HF range (LFRRI and HFRRI) will be calculated in normalized units and the ratio of LFRRI/HFRRI will be used as a measure of sympatho-vagal balance. We will also calculate the standard deviation of normal-to-normal interval (SDNN) and the root mean square of successive differences (RMSSD) indexes, given their established study in PWE.[11, 12]

2. Cardiorespiratory Fitness:

a. Maximum oxygen uptake (VO₂ max)

i. Cardiopulmonary exercise test using a modified Balke protocol[55, 56] on a treadmill

b. 6-minute walk test (6MWT)

Participants will undergo a 6 minute walk test at Visits 1 and 3, according to established guidelines[57]. This is a cost-effective and well-documented field test for assessing functional exercise capacity and response to medical interventions in diverse patient groups, and predicts cardiorespiratory fitness among healthy people[58].

3. Sleep:

a. Nightly average total sleep time (TST): will be collected from the Garmin activity tracker

b. Sleep quality will be assessed via the Pittsburgh Sleep Quality Index (PSQI)

c.

Analytical Plan

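### The Visit 2 telephone footnote lets the only baseline VO2 max test follow randomisation and disclosure of the arm, because nothing in the available text makes either wait for the test

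*Combined protocol and SAP*

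**What the plan says.** All references are to the combined protocol and SAP.

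- **Visit schedule table (under Follow-up Visits).** The column headed "Visit 2 Randomization Week 4" carries the randomisation mark. The exercise test is marked at Visits 2 and 3 only, and the Visit 4 text excludes it. Visit 2 therefore gives the only VO2 max value before the intervention.
- **Double-asterisk footnote to the table.** For cases where the visit is hard to arrange, the footnote reads: "V2 can be completed over the telephone with the exercise test being conducted at the first available timepoint and prior to the intervention period".
- **Text above the table.** "Due to batched enrollment, time between visits (especially Visits 2 and 3) may vary".
- **Baseline Period and Exclusion Criteria.** People with less than 75% complete diary or step days are not randomised. A completed exercise test is not named as a condition.
- **Arm 1 Exercise Intervention.** "Following randomization, the behavioral coach will contact the participants in this arm" to arrange the weekly meetings. No date is given for that contact.
- **Blinding.** It states that "participants will not be blinded as to whether they are in the intervention or control group". It adds that "The final analysis of activity data and heart rate variability (HRV) will also be performed by blinded assessors"; the treadmill test is not named.
- **Analytical Plan, Aim 3.** The change score is regressed on arm, with the baseline score as a covariate. The resulting effect sizes and variability are meant for planning a larger trial.
- **Appendix list.** A coaching manual and a handout for use after randomisation are listed but not reproduced.

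**The concern.** A baseline used for adjustment should be fixed before the participant knows the arm. A treadmill test for maximum oxygen uptake depends on how hard the participant is willing to work, and someone who has just been told the arm may push more or less than they otherwise would. The footnote's deadline rules out a training effect on the baseline value. It does not rule out an effect of knowing the assignment.

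If effort shifted differently in the two arms, the arm estimate for VO2 max would carry part of that difference. The estimate is exploratory, but the plan intends to use it to size a later trial.

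**Working it through.** **1. Order of events.** A treadmill test cannot be done by telephone. When Visit 2 is a telephone visit, the ordinary reading is that its other procedures, including randomisation, go ahead and the test is deferred. Three orders all comply with the footnote:

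- test, then randomisation, then disclosure;
- randomisation, then test, then disclosure;
- randomisation, then disclosure, then test.

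Only the third exposes the baseline. No available passage excludes it. Coach contact after randomisation makes it plausible, and the variable spacing between visits under batched enrolment means the wait before the intervention need not be short. The last two statements are inferences; the documents do not state when the arm is disclosed.

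**2. How a shifted baseline reaches the estimate.** The plan gives no figure to reproduce here, so what follows is illustration. Let b be the slope of follow-up VO2 max on baseline. Let p1 and p0 be the shares of arm 1 and control tested after disclosure, and s1 and s0 the baseline effort shifts in those participants, in SD units. Subtracting baseline from follow-up changes only the baseline coefficient (from b to b − 1). The arm coefficient is therefore the same in the change-score and follow-up models. A baseline shift contributes

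bias = −b × (p1·s1 − p0·s0).

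**3. Assumed inputs.** b = 0.8, p1 = p0 = 0.3, s0 = 0. None of these is in the documents.

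- s1 = +0.2: −0.8 × (0.3 × 0.2) = −0.048 SD.
- s1 = −0.2: +0.048 SD.

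Simulation gave −0.048 and +0.048.

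**4. Against the precision available.** The Sample Size section gives up to 40 at 2:1, so about 27 and 13. Taking b as the correlation (equal SDs at both visits):

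SE = √(1/27 + 1/13) × √(1 − 0.8²) = 0.338 × 0.6 = 0.20 SD.

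The ratio is 0.048 / 0.203 = 0.24, about a quarter of a standard error.

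**5. Range.** The 30% share in each arm and a shift in arm 1 only are kept.

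| b | s1 | Size of bias (SD) | SE (SD) | Bias / SE |
|---|---|---|---|---|
| 0.5 | 0.1 | 0.5 × 0.3 × 0.1 = 0.015 | 0.292 | 0.05 |
| 0.8 | 0.2 | 0.8 × 0.3 × 0.2 = 0.048 | 0.203 | 0.24 |
| 0.9 | 0.3 | 0.9 × 0.3 × 0.3 = 0.081 | 0.147 | 0.55 |

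The sign follows the sign of s1, which is unknown.

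**6. Reach.** The 6-minute walk test and the questionnaires have their baseline at Visit 1, before randomisation. The primary step endpoints and the ActivPAL endpoints do not use the treadmill test.

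**The case against.** The strongest reply is that the problem needs a chain of events: a scheduling exception, then disclosure before the test, then effort that depends on the arm. It then touches one exploratory endpoint in a feasibility trial of up to 40. The footnote already keeps the test ahead of the intervention, and the 6-minute walk test gives a second fitness measure with a clean baseline. The coaching manual and the post-randomisation handout may set the order in practice. All of this stands. It limits the point to what the available text leaves open and keeps its weight low. It does not close the gap, because no rule in that text does so.

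A reader might infer that the protocol requires randomisation before the test, or that this is the usual sequence. The documents do not support that: the footnote is an exception, and a test before allocation also complies with it.

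A reader might also infer that the treadmill data have no blinding at all. The Blinding section does say, without naming a measure, that those processing the data will not know the arms. That wording may extend to the treadmill data. It concerns processing, though, and cannot prevent a participant's own knowledge from affecting effort.

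**Conclusion.** The point holds as a gap in the stated order of events: the text permits an arm-aware baseline VO2 max test and contains nothing to prevent it. Confidence is high in that reading of the text and does not extend to any consequence.

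It would go too far to say that the VO2 max result will be biased, or biased in favour of the intervention. The documents give no telephone share, no effort shift and no slope, so neither size nor direction can be stated. The figure of about 0.05 SD is an illustration under assumed inputs. Much larger values arise only if every baseline test is assumed to follow disclosure (at b = 0.9 and a 0.3 SD shift, 0.27 SD or 1.83 standard errors), which a footnote for scheduling difficulty does not suggest.

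It would also go too far to extend the point to the feasibility conclusions, since the primary and secondary endpoints do not depend on this test. Effort at the Visit 3 test, when participants know their arm, is a separate matter that the change below does not address. The point is a cheap improvement worth considering, not a flaw that threatens the trial.

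**What to change.** **Order.** Amend the footnote and the Visit 2 procedure so that randomisation, or at least release of the assignment to participant and coach, follows completion of the baseline exercise test. The schedule also marks "HRV measurement" at Visit 2, and the methods require that "Continuous heart rate will be recorded while the participant is breathing normally in seated position for 10 minutes using Faros 180 heart rate monitor", which a telephone visit cannot provide. If that recording is deferred with the test, apply the same order to it.

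**Dates.** Record the date of the test and the date of disclosure, so that any exposure can be counted.

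**Participants already handled under the present footnote.** An optional VO2 max sensitivity analysis may exclude everyone who had a telephone Visit 2, where that status was fixed before allocation. It should not exclude by whether the test followed disclosure, because that timing arises after randomisation and may differ by arm.

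**Cost.** One sentence in the footnote and one in the procedure, with no extra test or staff. The test must already precede the intervention, so what moves is the notice of assignment. Some assignments would be released later, which could delay forming the batched coaching groups of 2 to 8. The number affected is unknown.

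The sensitivity analysis loses precision. From arm sizes alone, relative to √(1/27 + 1/13) and with assumed exclusion counts:

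- 3 excluded (25 and 12 left): √(1/25 + 1/12) gives a ratio of 1.04;
- 6 excluded (23 and 11 left): √(1/23 + 1/11) gives 1.09;
- 12 excluded (19 and 9 left): √(1/19 + 1/9) gives 1.20.

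The standard error therefore rises by about 4%, 9% and 20%.

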- Focal or generalized epilepsy, as determined clinically by a WFBH epileptologist with no significant consideration of an alternative diagnosis
- Active epilepsy with at least 1 observable seizure in the 6 months prior to screening
- Access to a smartphone with application capabilities
- Internet access or cellular data plan to attend virtual sessions
- Able to ambulate independently

Exclusion Criteria

- Diagnosis of nonepileptic or psychogenic spells
- Seizures associated with falls with injury (such as atonic seizures)
- Currently active ≥ 30 min on 3 or more days per week or > 5000 steps/day during the baseline period
- Medical conditions that would limit ability to participate in an exercise intervention including:
 - Stage III or IV Congestive Heart Failure (CHF)
 - End-stage Renal Disease
 - Severe dementia or significant cognitive impairment that precludes participation in the intervention or limits ability to follow the study protocol
 - Uncontrolled hypertension (HTN) defined as systolic blood pressure greater than 180 mmHg and diastolic blood pressure greater than 110 mmHg at rest
 - Severe arthritis, amputations, or orthopedic problems that limit ambulatory ability
- Currently pregnant or plan to become pregnant during the study period (16 weeks)
- An active Central Nervous System (CNS) infection, demyelinating disease, degenerative neurologic disease or any CNS disease deemed to be progressive during the course of the study that may confound the interpretation of the study results
- Any clinically significant psychiatric illness, psychological, or behavioral problems that would interfere with the subject's ability to participate in the study.
- Unwilling or unable to comply with all study visits and procedures
- Participants who have $<75\%$ complete days of seizure recording in the study diary or step data via the Garmin device will not be randomized.

Sample Size

Up to 40 subjects will be enrolled, with a 2:1 ratio of intervention to control group randomization to best address aims 1 and 2.

Interventions and Interactions

Protocol version:

Template updated 9.24.14

All participants will wear a Garmin device and keep a study diary throughout the duration of the study. In addition, they will wear an ActivPAL 4 for 1 week at the end of the baseline, intervention, and maintenance periods. This will be mailed to them for each of the three recording periods along with written instructions (attachment 8).

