3. Exploratory Objectives: Exploratory Effectiveness: For exploratory efficacy purposes, we will also gather pre- and post- intervention data on seizures, depression, anxiety, physical functioning, quality of life, and social cognitive mediators of behavior change via the following:

a. Exploratory Endpoints

i. Effects on seizures

1. Seizure frequency via study diary report

This has been shown to be a reliable and standard way of recording seizures in epilepsy studies. For the purposes of evaluating a change in seizure frequency, the number of seizures during the final 4 weeks of the intervention will be compared to the number of seizures during the 4-week baseline. The diaries will be returned via electronic data capture in redcap. Participants will be reminded to complete and return the diary via automated text and/or email. If diaries are not received, the participant will be called and prompted to return the study diary.

2. Seizure severity via the Liverpool seizure severity scale (LSSS)

ii. Effects on mood:

1. Depression scores

Participants will complete the Neurological Disorders Depression Inventory for Epilepsy (NDDI-E)[47]. This will be performed in-person at visits 1 and 3 only (monitoring and management of expression of suicidal ideation is outlined under Section VI below). This will be reviewed by study personnel and documented in the *Review Assurance of the NNDI-E* form

2. Anxiety scores

Participants will complete the Generalized Anxiety Disorder (GAD-7)[48, 49] in person at Visits 1 and 3 and remotely via redcap survey at Visit 4.

3. Stress scores (PSS)

Participants will complete the Perceived Stress Scale (PSS) in person at Visits 1 and 3 and remotely via redcap survey at Visit 4.

iii. Effects on quality of life

1. Quality of Life

Participants will complete the Quality of Life in Epilepsy-31 (QOLIE-31)[50]. This will be given in person as Visits 1, and 3, and remotely via emailed redcap survey link at Visit

2. Medication side effects

Participants will complete the Adverse Event Profile (AEP) at Visits 1 and 3 and remotely via emailed redcap survey link at Visit 4

iv. Effects on social cognitive theory constructs

1. To evaluate the influence of social cognitive constructs on behavior change in this population, participants will complete the Exercise Self-

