Aim 1 To assess Feasibility, we will look at (1) adherence and (2) sustainability. Adherence, defined as the proportion of participants who achieve their assigned step goal (as measured by average daily steps via the Garmin device) over the last 4 weeks of the intervention period, will be calculated and 95% binomial confidence intervals generated. Sustainability will be calculated similarly for the final 4 weeks of the maintenance period. In each case, we will utilize a one-sided 95% confidence interval to estimate the lower bound for adherence and sustainability rates to inform future studies.

Aim 2 To assess exercise *intensity*, we will use descriptive statistics to describe the time spent in sedentary, light, and moderate to vigorous PA. We will generate confidence intervals to evaluate if the achieved intensity is within the range recommended by the AHA (150 min of moderate or 75 min of vigorous activity per week).[59] To assess acceptability, arm 1 will answer a questionnaire at the end of the 12 week intervention about the acceptability, tolerance and satisfaction with the exercise intervention. For the main endpoint, we will use the question “How satisfied were you with the exercise intervention?” with scale of 1=VERY UNSATISFIED, 2=UNSATISFIED, 3=NEUTRAL, 4=SATISFIED, 5=VERY SATISFIED. We will calculate the proportion of subjects who answer 4 or above.

To address Aim 3 (exploratory evaluation of effects epilepsy and epilepsy associated comorbidities), we will compute change scores in seizure frequency, severity (LSSS), anxiety (GAD-7), depression (NDDI-E), medication side effects (AEP), cardiorespiratory fitness (VO2 max and 6MWT), heartrate variability (HRV), sleep (total sleep time per night) and quality of life (QOLIE-31) pre- and post-intervention. We will use multivariable linear regression models modeling change score as the outcome, with intervention assignment as the main effect of interest and baseline scores as a confounding variable. We will use estimates of the effect sizes and variability for planning and power of a larger trial. For HRV parameters, we will look at high and low frequency indices, standard deviation of normal-to-normal interval (SDNN) and the root mean square of successive differences (RMSSD) indices, given their established study in PWE.[11, 12]

Similarly, we will explore for effects on social cognitive mediators of behavior change (scores on EXSE, MOEES, and EGS), following the same modeling approach.

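### Participants at about one to two seizures per six months will mostly record none in both 4-week windows, so a 12-week seizure rate is worth reporting beside the final-4-week outcome

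*Combined protocol and SAP*

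**What the plan says.** - **Entry.** The Inclusion Criteria ask for "Active epilepsy with at least 1 observable seizure in the 6 months prior to screening". The baseline check before randomization concerns data completeness, not seizure count: "participants who have <75% complete days of seizure recording or step data via the Garmin will not be randomized".
- **Data collected.** Under Interventions and Interactions, "All participants will wear a Garmin device and keep a study diary throughout the duration of the study". A note to the visit schedule adds that "the study diary will also be returned daily and reviewed by weekly by a member of the study staff". For Arm 1, "Participants in this arm will undergo a 12-week physical activity program".
- **Outcome.** In Outcome Measure(s), under the exploratory seizure endpoint, "the number of seizures during the final 4 weeks of the intervention will be compared to the number of seizures during the 4-week baseline". The Baseline Period text calls a 4-week baseline standard in epilepsy trials. No reason is given for the length of the post-baseline window.
- **Analysis.** The Analytical Plan for Aim 3 uses linear regression, "modeling change score as the outcome, with intervention assignment as the main effect of interest and baseline scores as a confounding variable", and intends the resulting effect sizes and variability for planning a larger trial.
- **Size.** "Up to 40 subjects will be enrolled, with a 2:1 ratio of intervention to control group randomization".

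**The concern.** The entry criterion allows rates so low that 28 days will often contain no seizure. For those participants the change score is usually zero whether or not the intervention works. They then add little to the seizure effect estimate, although eight further weeks of diary data exist for each of them.

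Aim 3 is meant to supply effect-size and variability estimates for a larger trial. If only the 4-week window is reported, planners see one variance, which includes the counting noise of a short window. They cannot judge whether a longer treatment-period outcome would serve the next trial better. Aims 1 and 2 are not affected.

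**Working it through.** The plan gives no seizure-based sample size, power or variance, so there is no figure of its own to reproduce.

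**Step 1: weeks not used.** 12 − 4 = 8 of 12 intervention weeks do not enter this outcome.

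**Step 2: chance of zero in both windows.** Assume Poisson counts, a constant rate, no treatment effect, and six months = 26 weeks. With k seizures per 26 weeks, the mean per 4 weeks is 4k/26. The chance of none in baseline and in the final 4 weeks is exp(−8k/26). The chance of none in baseline and in all 12 intervention weeks is exp(−16k/26).

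| k per 6 months | Mean per 4 weeks | None in one 4-week window | None in baseline and final 4 weeks | None in baseline and 12 weeks |
|---|---|---|---|---|
| 1 | 0.154 | 85.7% | 73.5% | 54.0% |
| 2 | 0.308 | 73.5% | 54.0% | 29.2% |
| 3 | 0.462 | 63.0% | 39.7% | 15.8% |
| 4 | 0.615 | 54.0% | 29.2% | 8.5% |
| 6 | 0.923 | 39.7% | 15.8% | 2.5% |

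Zero in both 4-week windows is the majority result up to k = 26 × ln 2 / 8 = 2.25.

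Sensitivity: taking six months as 24 weeks gives 71.7% at k = 1 and 51.3% at k = 2. Negative binomial counts (dispersion 0.5–2, independent windows) give 74–77% and 56–62%.

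The background section quotes a 40% reduction from an uncontrolled study. Applied after baseline at k = 1, it moves the zero-in-both share only from 73.5% to exp(−0.154 × 1.6) = 78.2%.

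**Step 3: variance in a mixed population.** Let individual rates per 28 days be gamma-distributed with mean m and shape a (assumed; the documents give no distribution). Let w be the number of 28-day blocks after baseline: 1 for the plan's window, 3 for 12 weeks. With the baseline count in the model, the change score and the post-baseline rate have the same residual variance, m(1/w + s), where s = m/(m + a). The relative sample size needed is variance divided by effect squared. The 12-week rate therefore breaks even when its average effect, as a share of the late effect, equals the square root of the variance ratio.

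| m | a | s | 4 weeks | 12 weeks | Ratio | Break-even |
|---|---|---|---|---|---|---|
| 1 | 0.5 | 0.667 | 1.667 | 1.000 | 0.600 | 0.775 |
| 2 | 0.5 | 0.800 | 3.600 | 2.267 | 0.630 | 0.794 |
| 4 | 0.5 | 0.889 | 7.556 | 4.889 | 0.647 | 0.804 |
| 1 | 1 | 0.500 | 1.500 | 0.833 | 0.556 | 0.745 |

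Simulated values for these four cases agree (1.67 v 1.01, 3.58 v 2.25, 7.57 v 4.90, 1.50 v 0.83). The variance reduction is thus about 35–45%. The break-even share is about 74–81% (√0.55 = 0.74, √0.65 = 0.81).

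**Step 4: how much effect a 12-week average might keep.** Suppose the effect grows linearly for r weeks and then holds. The 12-week average is (r/2 + 12 − r)/12 of the late effect:
- r = 4: 10/12 = 83%, which favours 12 weeks.
- r = 6: 9/12 = 75%, about break-even.
- r = 8: 8/12 = 67%, which favours the final 4 weeks.

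The documents do not give the time course.

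**The case against.** The strongest defence is that the late window answers a sensible question: seizures once activity has reached its achieved level. Goals rise by about 20–30% at a time, only after successful weeks, towards 8,000 steps a day, and people above 5,000 at baseline are excluded. With every week successful, a start at 2,000 steps needs 8 increments at 20% or 6 at 30%; a start at 5,000 needs 3 or 2. The final 4 weeks are also the adherence window of Aim 1. This stands, and it is why the outcome should remain as defined.

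A reader might infer more than the documents support:
- **That the final-4-week outcome is wrong and a 12-week rate should replace it.** Step 4 shows that the gain in precision can be outweighed by dilution. Which dominates is unknown.
- **That most of the trial will show zero change.** One seizure in six months is a floor, not a typical rate, and the enrolled distribution is not given. The only rate quoted, 2.9 per week in a drug-resistant sample, makes zero in both windows negligible.
- **That weeks 1–8 go unused altogether.** The safety plan reviews the diary weekly for seizure increases. The weeks are left out of this outcome only.
- **That the 4-week variance is a wrong planning input.** If the larger trial keeps the same windows, it is the right one. The plan does not specify that trial's endpoint.

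**Conclusion.** The concern holds in a limited form. Participants at about one to two seizures per six months will mostly record none before and none after (73.5% and 54.0% under Poisson counts with no effect), and eight recorded weeks do not inform the seizure estimate. The share of such participants is unknown.

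The 35–45% variance reduction rests on assumed gamma-distributed rates of 1–4 per 28 days, about 6.5–26 per six months. That is a busier population than the one behind the zero-count figures, so the two results should not be combined. Neither shows that the 12-week rate is better overall; together they show that both windows are worth reporting. The endpoint is exploratory and the feasibility conclusions do not depend on it, so this is an optional, low-severity improvement.

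**What to change.** Keep the final-4-week comparison as defined. In the seizure-frequency item of Outcome Measure(s) and the Aim 3 paragraph of the Analytical Plan, add:

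1. A prespecified seizure rate per 28 days over all 12 intervention weeks, analysed with the same baseline adjustment.
2. Effect estimates and residual variances for both windows, side by side.
3. The number of participants with no seizure in baseline, in the final 4 weeks and in the 12 weeks, and the number with none in baseline and in each later window together.

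Planners of the larger trial can then weigh precision against dilution using observed data.

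The cost is some wording and one more exploratory analysis; the diary data are already collected. The 12-week rate includes the ramp-up weeks and may understate a late effect, which the retained outcome would show. The addition is also only a partial remedy: because the baseline stays at 4 weeks, 54.0% of participants at the entry floor would still show zero in baseline and in the 12 weeks.
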